9.3.3 Removal of Subjects from Therapy or Assessment

The investigator may discontinue study drug or withdraw the subject from the study at any time for safety or administrative reasons. The subject may decide to stop study drug or withdraw from the study at any time for any reason.

Subjects who discontinue taking study drug prematurely for any reason will undergo an ED Visit within 7 days of their last dose of study drug (see [Section 9.1.2.2](#)). Follow-Up Visits will also be scheduled 2, 4, 8, and 12 weeks after the last dose of study drug in the Core Study (see [Section 9.1.2.3](#)), and 4 and 12 weeks after the last dose of study drug in the OLE Phase (see [Appendix 6](#)). (revised per Amendments 04, 05 and 07)

The primary reason for discontinuation and all other reason(s) contributing to the subject's discontinuation from study drug(s) should be collected on the Subject Disposition eCRF page. In addition, the date of last dose of study drug(s) will be recorded on the Study Drug Dosing eCRF page. If a subject discontinues study drug and withdraws from the study at the same time, the ED Visit will be followed (see [Section 9.5.5](#)).

Safety-related criteria for discontinuation of study drug during the Core Study include the following: (revised per Amendments 07)

- a. A study drug discontinuation threshold will be set based on absolute counts of CD4 (T helper cells), CD8 (cytotoxic T cells), or CD19 (B cells). The discontinuation threshold will be set at below the level of the population-adjusted LLN (CD4=396 cells/ μ L; CD8=157 cells/ μ L; and CD19=74 cells/ μ L), at a level that represents a greater risk of opportunistic infection in the treated population. (revised per Amendment 02) For CD4 (T helper cells) the discontinuation threshold is 250 cells/ μ L. For CD8 (cytotoxic T cells) and CD19 (B cells) the discontinuation thresholds are 150 cells/ μ L and 50 cells/ μ L, respectively. Any subject who has CD4 (T helper cells), CD8 (cytotoxic T cells), or CD19 (B cells) absolute counts below the discontinuation threshold as confirmed by a repeat test conducted within 1 week of the initial test but who has no clinical signs or symptoms of infection, will have study drug temporarily suspended for at least 2 weeks but no more than 4 weeks. During this period of study drug suspension, lymphocyte subset counts and complete blood count (CBC) with differentials will continue to be tested weekly until CD4 (T helper cells), CD8 (cytotoxic T cells), and CD19 (B cells) have all returned to greater than the population-adjusted LLN after which time study drug can be resumed. Testing of lymphocyte subset counts and CBC with differentials is required weekly for 4 weeks following resumption of study drug administration. Temporary suspension and rechallenge with study drug is only permitted once for any given subject. If the lymphocytes and CD counts do not return to greater than the population-adjusted LLN within 4 weeks from the start of temporary suspension the subject will need to be permanently discontinued from study drug. (revised per Amendment 04)
- b. Subjects with CD4 (T helper cells), CD8 (cytotoxic T cells), or CD19 (B cells) absolute counts between the population-adjusted LLN and the discontinuation threshold will have lymphocyte subset counts performed on a weekly basis. (revised per Amendments 02 and 04) During the early stages of the treatment period, where visits are conducted weekly (ie, Visits 4, 5, 6, and 7), lymphocyte subsets are already scheduled to be measured on a weekly basis and so additional visits or blood draws are not required. (revised per Amendment 02) For these subjects, the decision as to whether the subject remains on study drug or is to be discontinued from study drug will be based upon clinical judgment and will take into account any clinical presentation in addition to the

lymphocyte subset counts. These subjects may continue with treatment if there is no clinical evidence of infection. They will be discontinued from study drug if they have infections of a moderate to severe intensity (eg, subjects whose infections are not localized, or are systemically unwell, or who require systemic anti-infective drug treatment).

Table 1 Study Drug Actions for Lymphocyte Subset Absolute Counts

| Lymphocyte subset absolute counts | Action | Decision to continue, discontinue, or temporarily suspend study drug |
|---|--|--|
| CD4 (T helper cells), CD8 (cytotoxic T cells), or CD19 (B cells) absolute counts below discontinuation threshold and no clinical signs or symptoms of infection | Retest within 1 week along with CBC with differentials | If retest performed within 1 week confirms lymphocyte subset counts below the discontinuation threshold, temporarily suspend study drug for between 2 and 4 weeks. Continue weekly testing of lymphocyte subsets and CBC with differentials. Rechallenge with study drug allowed when CD4 (T helper cells), CD8 (cytotoxic T cells), and CD19 (B cells) absolute counts all greater than population-adjusted LLN. Temporary suspension and rechallenge permitted only once for each subject. |
| CD4 (T helper cells), CD8 (cytotoxic T cells), or CD19 (B cells) absolute counts between population-adjusted LLN and discontinuation threshold | Lymphocyte subset counts (and CBC with differentials) to be performed weekly until lymphocyte subset counts return to \geq population-adjusted LLN | Decision will be based upon lymphocyte subset counts and clinical judgment |

LLN = lower limit of normal, CBC = complete blood count.

(Table revised per Amendments 02 and 04)

- c. Subjects with clinical evidence of infection will have their CD4 (T helper cells), CD8 (cytotoxic T cells), and CD19 (B cells) absolute counts measured. Blood and other biological samples will also be collected for investigations of infective pathogens (eg, serological tests, quantitative polymerase chain reaction, microscopy, and culture) where appropriate. In subjects with infection, if any of their absolute cell counts meets the discontinuation thresholds, study drug will be discontinued. All subjects with severe infections will be discontinued from study drug. All subjects with herpes zoster (shingles) or ocular herpes infections will be discontinued from study drug, regardless of severity of presentation. Subjects with mild or moderate infection may continue treatment with study drug unless otherwise clinically indicated or otherwise specified below. Specifically, when any of the CD4 (T helper cells), CD8 (cytotoxic T cells), and

CD19 (B cells) absolute counts are between the population-adjusted LLN and the discontinuation thresholds, subjects with infections of moderate intensity will be discontinued from study drug (eg, subjects whose infections are not localized, or subjects who are systemically unwell, or who require systemic anti-infective drug treatment). All subjects with infection who are discontinued from study drug will be followed for a period of 12 weeks or until the infection resolves/ stabilizes or until the CD4 (T helper cells), CD8 (cytotoxic T cells), and CD19 (B cells) absolute counts have returned to greater than population-adjusted LLN (whichever comes latest). (revised per Amendments 02 and 04)

Table 2 Study Drug Actions for Lymphocyte Subset Absolute Counts and Infection

| Criterion | Severity of Infection | | | |
|--|--|---|---|------------------------|
| | None | Mild | Moderate | Severe |
| CD4 (T helper cells), CD8 (cytotoxic T cells), or CD19 (B cells) absolute counts below discontinuation threshold | If confirmed with repeat testing within 1 week, then temporarily suspend study drug as per instructions above. | Discontinue study drug | Discontinue study drug | Discontinue study drug |
| CD4 (T helper cells), CD8 (cytotoxic T cells), or CD19 (B cells) absolute counts between population-adjusted LLN and discontinuation threshold | May continue treatment with study drug unless discontinuation is clinically indicated | May continue treatment with study drug unless discontinuation is clinically indicated | Discontinue study drug | Discontinue study drug |
| CD4 (T helper cells), CD8 (cytotoxic T cells), or CD19 (B cells) absolute counts always > population-adjusted LLN | May continue treatment with study drug unless discontinuation is clinically indicated | May continue treatment with study drug unless discontinuation is clinically indicated | May continue treatment with study drug unless discontinuation is clinically indicated (See (e) for exception) | Discontinue study drug |

LLN = lower limit of normal.

(Table revised per Amendments 02 and 04)

- d. A subject with any skin rash of moderate to severe intensity, or any rash lasting more than 72 hours regardless of severity (see (e) for exception), will be discontinued from study drug and a dermatological consult will be requested regardless of whether the rash is considered drug-related or due to other causes. For cases where the investigator suspects a drug rash, regardless of severity, the subject will be discontinued from study drug, a dermatological consult will be requested, and a skin biopsy will be performed to confirm the diagnosis. The skin rash will be treated as per standard care and will be followed up until resolution regardless of etiology or severity.

- e. Subjects who develop moderate to severe oral or genital herpes should be discontinued from study drug. Subjects who develop a mild case of oral or genital herpes may remain on study drug even if the event lasts more than 72 hours.
- f. Development of any of the following features on MRI: vasogenic edema, macrohemorrhage, an area of superficial siderosis, or a symptomatic microhemorrhage. If discontinued from study drug, subjects will undergo an ED Visit within 7 days after discontinuation and will attend the Follow-Up Visits 2, 4, 8, and 12 weeks after the last dose of study drug. They will also undertake an Unscheduled Visit (with MRI) at approximately 4 weeks after the visit at which such MRI features were first identified. An MRI will also be performed at approximately the time of the final Follow-Up Visit (Visit 20). Additional visits for safety may be arranged if clinically indicated in the opinion of the investigator, including after 12 weeks after the last dose of study drug. At any time during the treatment period, subjects who have asymptomatic, treatment-emergent microhemorrhages as detected by MRI, but none of the features which merit discontinuation of treatment (ie, vasogenic edema, macrohemorrhage, an area of superficial siderosis, or a symptomatic treatment-emergent microhemorrhage) may continue with treatment. These subjects will have safety assessments (including MRI) at approximately 4 weeks after the visit at which such MRI features were found. They will also continue with the scheduled MRI scans. Additional unscheduled MRI scans may be arranged on an individual subject basis in discussion with the study medical monitor. (revised per Amendment 04)
- g. A postdose ECG with an average QTcF interval >500 msec from triplicate ECGs
- h. A postdose ECG with a QTcF interval increase from baseline >60 msec and a QTcF interval >450 msec as demonstrated from triplicate ECGs
- i. Any seizure (motor or non-motor)
- j. Pregnancy

Safety-related criteria for discontinuation of study drug during the OLE Phase are provided in [Appendix 6](#). (revised per Amendment 07)

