9.2.5 Clinical Risks and Mitigation Strategy

A number of safety aspects have been built into the design of this study in light of the preclinical and clinical safety data with elenbecestat (E2609), and to mitigate clinical risk in the progression from 14 days of dosing in the MAD study to 18 months of Core Study treatment and 24 months of OLE Phase treatment in this Phase 2 study. (revised per Amendment 07) These safety aspects include the following:

- Immunology-related and infection-related exclusion criteria for both the Core Study and the OLE Phase (revised per Amendment 07)
- Review of unblinded safety data by an independent DSMB at regular intervals
- Safety criteria for study drug discontinuation based on CD4 (T helper cells), CD8 (cytotoxic T cells), CD19 (B cell) during the Core Study and absolute lymphocytes during the OLE Phase (revised per Amendment 07)
- Safety criteria for study drug discontinuation during the Core Study and OLE Phase based on skin rash, reoccurrence of herpes virus infections including any oral herpes, genital herpes or shingles, other infections, MRI changes, ECGs, and pregnancy. (revised per Amendment 07)

In addition to the features above, other safety aspects of this study designed to mitigate clinical risk include the following:

- Blinded safety data will be monitored by Eisai at regular intervals during the course of the study
- Routine safety assessments will include the monitoring and recording of all AEs and SAEs, monitoring of hematology, blood chemistry, and urinalysis, measurement of vital signs, regular ECGs, physical and neurological examinations, and dermatological assessments at regular intervals. (revised per Amendment 07) AEs that might indicate signals of possible drug abuse potential will require a detailed follow-up. Subjects reporting AEs relating to abnormal dreams, nightmares, or sleep terror will be questioned on the frequency and impact of these events. To assess potential immunomodulatory effects, peripheral blood mononuclear cells (PBMCs) will be collected at baseline, during treatment, and posttreatment.

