10. Subjects with hepatic impairment, with total bilirubin greater than $1.5 \times$ upper limit of normal (ULN) or International Normalized Ratio (INR) greater than 1.7 at Screening or Baseline. Subjects with Gilbert's syndrome need not be excluded.
11. Any contraindications to MRI or PET scanning, including cardiac pacemaker/ defibrillator or ferromagnetic metal implants (eg, in skull; cardiac devices other than those approved as safe for use in MRI scanners). Subjects who require sedation for MRI or PET scanning as per local guidelines need not be excluded.
12. Any contraindications to LP for CSF sampling (eg, lower spinal malformation on physical examination, local spinal infection or other abnormality, including but not

- limited to obesity). Only applicable to subjects consenting to CSF sample collection (revised per Amendment 02)
13. Severe visual or hearing impairment that would prevent the subject from performing psychometric tests accurately
 14. History of Ig deficiency or other immunodeficiency disorders (including subjects known to be human immunodeficiency virus positive)
 15. Subjects with chronic viral hepatitis
 16. A history of tuberculosis (TB). Subjects with no history of TB will be tested for previous TB exposure (eg, positive tuberculin skin test, interferon gamma release assay or other locally accepted tests) and a positive test will be exclusionary.
 17. A history of ophthalmic shingles
 18. A history of ocular herpes simplex virus (HSV) infection
 19. Any live vaccine in the 3 months before randomization.
 20. Any active infection within the last 4 weeks prior to randomization. For such cases, the timing of randomization can be extended (up to 4 weeks) to allow the infection to resolve; psychometric tests (eg, MMSE, CDR) and safety laboratory tests conducted at Visit 2 must be repeated. (revised per Amendment 02)
 21. Any chronic inflammatory disease that is not adequately controlled or that requires systemic or ocular immunosuppressive or immunomodulatory therapy. Subjects with:
 - a. Seasonal or perennial allergic rhinitis, asthma or chronic obstructive pulmonary disease where the condition is considered to be stable and adequately controlled by inhaled steroids need not be excluded.
 - b. Hashimoto's thyroiditis but who are stable on thyroid replacement therapy and not on systemic immunosuppressive therapy need not be excluded.

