9.4 Treatments

9.4.1 Treatments Administered

For the Core Study, the test drug is elenbecestat (E2609) and the control drug is placebo. (revised per Amendments 07) All study drugs are to be administered orally, QD, with food.

Treatments to be administered during the Core Study are 5, 15, and 50 mg elenbecestat (E2609) or placebo prior to the implementation of Amendment 06, and 50 mg elenbecestat (E2609) or placebo after the implementation of Amendment 06 as shown in [Figure 1](#). (revised per Amendments 01, 05, 06, and 07) Study treatment will begin on Day 1 (at the study site) following Randomization and will continue for approximately 78 weeks. Please refer to [Table 7](#) and [Section 9.5.1.4.1](#) for specific information on drug administration on days when PK sampling is to be performed.

Treatments to be administered during the OLE Phase are described in [Appendix 6](#). (revised per Amendment 07)

Study drug doses will remain the same for each individual subject unless the interim PK/PD analysis determines that an entire dose level requires adjustment ([Section 9.4.4](#)). See [Section 9.3.3](#) for safety-related discontinuation criteria of study drug. If a subject develops a concurrent illness during the treatment period, the investigator should discuss with the medical monitor on whether dosing with study drug needs to be temporarily suspended. As a general clinical guideline, dosing with study drug may be resumed after resolution or stabilization of the concurrent illness, after discussion with the medical monitor.

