The PK/PD modeling described above, which was conducted using data obtained from healthy volunteers, has also been supported by modeling of data from subjects with an underlying AD pathology (Study 101). Furthermore, external data with another BACE1 inhibitor (MK-8931) showed a similar PD effect in AD patients as in healthy volunteers (Forman, et al., 2013). Therefore we are confident that the modeling of elenbecestat (E2609) effects in healthy subjects will be applicable for both MCI/Prodromal and mild to moderate AD dementia patients. (revised per Amendment 01)

The exposure of the highest dose in this study (50 mg QD tablet administered with food) is less than that of the 100 mg QD dose (capsule administered fasted) in Study 002.

The 100 mg QD dose administered for 14 days in Study 002 was well tolerated with no clinically significant changes in laboratory parameters, vital signs, or ECG parameters. On Day 15, for the 100 mg QD cohort in Study 002, there was a reduction of CD4 lymphocyte counts compared with placebo (CD4 lymphocyte counts on elenbecestat (E2609) decreased by 3.1% from baseline, whereas the placebo control showed an increase of 8.7%), but this decrease was less than that observed at doses of 200 mg (22.9% decrease) or 400 mg (17.3% decrease). No subject had infections or drug rash while receiving elenbecestat (E2609) 100 mg QD or at lower doses in Study 002, whereas at 200 and 400 mg QD, 4 subjects had symptomatic orolabial HSV1 relapses and 2 subjects at the highest dose had drug rash. The highest dose for Study 202 of 50 mg QD (tablet administered with food) is therefore expected to have a similar or better safety profile compared with the 100 mg QD capsule (administered fasted) in Study 002. Specific exclusion criteria, blinded and unblinded safety monitoring procedures, and safety criteria for discontinuation from study drug are included in this study in order to mitigate any immunology-related risk with elenbecestat (E2609), particularly in light of the progression from 14 days of dosing (Study 002) to 18 months of dosing in this study.

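### Table 2 of section 9.3.3 omits the mandatory stop for herpes zoster and ocular herpes from its three cells that let infected subjects continue

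*Protocol*

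**What the plan says.** Protocol section 9.3.3, criterion (c), states the rule without qualification: "All subjects with herpes zoster (shingles) or ocular herpes infections will be discontinued from study drug, regardless of severity of presentation". Section 9.2.5 agrees; among the grounds for discontinuation it lists "reoccurrence of herpes virus infections including any oral herpes, genital herpes or shingles".

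Table 2 follows criterion (c). Its rows are three lymphocyte-count bands: below the discontinuation threshold, between the threshold and the population-adjusted lower limit of normal (LLN), and always above that limit. Its columns are no, mild, moderate and severe infection. The cell for moderate infection with counts above the limit reads: "May continue treatment with study drug unless discontinuation is clinically indicated (See (e) for exception"). Two mild-infection cells carry the same permission with no flag. The table's notes define LLN and record the amendments; they do not mention zoster or ocular herpes.

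Criterion (e), to which the flag points, says: "Subjects who develop moderate to severe oral or genital herpes should be discontinued from study drug". It then lets mild oral or genital herpes stay on drug. It names neither zoster nor ocular herpes.

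**The concern.** The table and the criterion above it give different instructions for the same event. Under (c) the stop is compulsory. Under the three cells it depends on whether the investigator finds discontinuation clinically indicated.

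The flag in the moderate cell makes a misreading more likely. It shows that the table does carry infection-specific exceptions, and a reader who follows it finds a herpes rule without zoster or ocular herpes. That reader could take the list of exceptions as complete. Criterion (c) itself gives limited help: its permission for mild or moderate infection yields to clinical indication and to what is specified further down, whereas the zoster and ocular herpes rule stands in the sentence before.

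A subject who is discontinued has an Early Discontinuation Visit within 7 days (section 9.3.3). Follow-up then lasts 12 weeks, or until the infection resolves or stabilises, or until counts recover, whichever is latest (criterion (c)). The subject may not restart study drug (section 9.5.5). A subject kept on drug, or only suspended, is handled differently.

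**Working it through.** The protocol offers no figure to reproduce. The check is a cell-by-cell reading of Table 2 against criteria (c), (d) and (e), followed by a rough bound on the number of events.

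**Cells of Table 2**

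| Count band | Mild | Moderate | Severe |
|---|---|---|---|
| Below threshold | stop | stop | stop |
| Between threshold and LLN | may continue | stop | stop |
| Always above LLN | may continue | may continue, flag to (e) | stop |

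- All cells: 3 bands × 4 columns = 12. Infection cells: 3 × 3 = 9.
- Stop: 3 + 2 + 1 = 6 of 9 (67%). These agree with (c).
- May continue: 0 + 1 + 2 = 3 of 9 (33%).
- Of those 3, one carries a flag, and it goes to (e). None excepts zoster or ocular herpes.

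**What other provisions catch**

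- Criterion (d) stops any moderate or severe rash and "any rash lasting more than 72 hours regardless of severity (see (e) for exception"). It misses a mild zoster rash in its first 72 hours and ocular herpes without rash.
- Section 9.3.2 excludes subjects with "A history of ophthalmic shingles" or of ocular herpes simplex. It does not exclude earlier non-ocular shingles and cannot prevent new disease.
- Section 9.5.1.5.1 requires a detailed description of zoster to the Medical Monitor. Section 9.5.1.5.2 makes ocular herpes always serious, and section 9.5.4.1 requires serious events to be reported within 24 hours. These are reporting duties, not instructions to stop.
- For concurrent illness, section 9.4.1 says "the investigator should discuss with the medical monitor on whether dosing with study drug needs to be temporarily suspended", with resumption possible afterwards. Under (c) the drug is stopped for good.

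What remains is mainly mild zoster rash within 72 hours and non-severe ocular herpes without rash.

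**Bound on events**

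- Treatment lasts 78 weeks: 78/52 = 1.5 years.
- Randomised subjects are 60 ± 20%, that is 48 to 72. Full dosing gives 48 × 1.5 = 72, 60 × 1.5 = 90 and 72 × 1.5 = 108 subject-years.
- The protocol gives no rate for zoster or ocular herpes. Assuming 1 to 3 cases per 100 subject-years: 72 × 0.01 = 0.7 up to 108 × 0.03 = 3.2 cases.

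This range covers all arms, placebo included, and full dosing from the first day. It is taken before the other provisions and before restriction to the three cells. It is a ceiling on relevant events under the assumed rate, not an estimate of subjects wrongly continued.

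**The case against.** The strongest reply is that nothing is missing from the rule. Criterion (c) is categorical and stands immediately above the table, and section 9.2.5 repeats that shingles is a ground for stopping. The three cells do not forbid stopping. Table 2 has no pathogen dimension and does not flag rash rule (d) either, so it is plainly not a complete list of stops. Other sections send sites to section 9.3.3 as a whole, and section 9.4.1 does so before giving its general guideline on concurrent illness. On this view an error requires a site to use the table while ignoring the paragraph it belongs to.

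The clinical evidence is also indirect. The herpes events in section 9.4.4 are of another kind and at higher doses: "at 200 and 400 mg QD, 4 subjects had symptomatic orolabial HSV1 relapses". That section reports no infections at 100 mg or below, and the top dose here is 50 mg.

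These points hold as to size. They make harm unlikely and keep the matter minor. They do not remove the mismatch: a table whose title says it gives study drug actions leaves to judgement what (c) makes compulsory, and its one herpes pointer leads to a rule that omits these two infections. Nor does the absence of a flag for (d) help, because it shows a table that is incomplete in a second respect. It is also true that no clause ranks text over table. That (c) governs is inferred from its wording.

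**Conclusion.** The concern holds. Three of the nine infection cells in Table 2 state an action that is wrong for herpes zoster and ocular herpes when read against criterion (c), and none carries the exception. The omission is certain from the text. Its consequence is small and cannot be measured from the protocol: the 0.7 to 3.2 cases rest on an assumed rate and ignore the provisions that would catch most of them. The conclusion assumes that (c) prevails over the table, which is the natural reading of a rule that admits no exception for severity. This is a minor patient-safety consistency correction that should be made; it does not bear on any statistical result. It concerns the Core Study only, since Appendix 6 sets separate stopping criteria for the extension.

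**What to change.** Add a footnote to the three infection cells of Table 2 that permit continuation (mild with counts between the threshold and LLN, mild with counts above LLN, and moderate with counts above LLN). Suggested wording: *Herpes zoster or ocular herpes: discontinue study drug regardless of severity or cell count, per (c).* Keep the existing flag to (e). Criterion (c) needs no change.

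The cost is one table footnote at the next amendment and a short memo to sites. It affects only dosing still to come and changes no data collection, visit or analysis.
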